### 5.1.3. ATP cohort for analysis of immunogenicity

The ATP cohort for analysis of immunogenicity will include all evaluable subjects from the ATP cohort for analysis of safety:

- Who meet all eligibility criteria.
- Who comply with the procedures and intervals defined in the protocol.
- Who are within the maximum interval allowed as defined in the protocol.
- Who do not meet any of the criteria for elimination from an ATP analysis (refer to Section 6.7.2 from protocol) during the study.
- Who did not receive a product leading to exclusion from an ATP analysis as listed in Section 6.7.2 from protocol.
- Who did not present with a medical condition leading to exclusion from an ATP analysis as listed in Section 6.8 from protocol.
- Who have the cord blood collection at least 21 days post-vaccination.
- For whom data concerning immunogenicity endpoint measures are available. This will include subjects for whom assay results are available for antibodies against at least one study vaccine antigen component one month after vaccination i.e. Visit 3 in the cord blood sample.

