3. STUDY DESIGN OVERVIEW (AMENDED: 15 JULY 2015)

N: Number of subjects planned to be enrolled

Pre-vacc: Blood sample to be collected before the dose of the booster vaccination in pregnant women (Visit 1).

Post-vacc: Blood sample to be collected one month after the booster vaccination in pregnant women (Visit 2).

Protocol waivers or exemptions are not allowed with the exception of immediate safety concerns. Therefore, adherence to the study design requirements, including those specified in the outline of study procedures (Section 5.5), are essential and required for study conduct.

- Experimental design: Phase IV, observer-blind, randomised, placebo-controlled, multi-centric, multi-country study with two cross-over groups. ***All eligible household contacts of the infants born to pregnant women enrolled in Spain will be eligible to receive a single dose of Boostrix as part of an assessment of cocooning.***
- Duration of the study: The intended duration of the study will be approximately 5 months for each subject.
 - Epoch 001: Booster vaccination starting at Screening visit (Day -14 to 0) and ending at Visit 4 (post-delivery Month 2).
- Study groups: The study groups are defined as follows:
 - dTpa Group: This group will consist of pregnant women who will receive a single dose of *Boostrix* at 27-36 weeks (i.e. completed 27 weeks until 36 weeks) of gestation (Visit 1) and will receive a dose of the placebo post-delivery (within 72 hours).

- Control Group: This group will consist of pregnant women who will receive a single dose of placebo at 27-36 weeks (i.e. completed 27 weeks until 36 weeks) of gestation (Visit 1) and will receive a dose of *Boostrix* post-delivery (within 72 hours).

The study groups and epoch foreseen in the study are presented in [Table 1](#).

Table 1 Study groups and epoch foreseen in the study

Study groups	Number of subjects	Age (Min/Max)	Epoch
			Epoch 001
dTpa Group	340	18 years - 45 years	x
Control Group	340	18 years - 45 years	x

The study groups and treatment foreseen in the study are presented in [Table 2](#).

Table 2 Study groups and treatment foreseen in the study (Amended: 15 July 2015)

Treatment name	Vaccine name	Study Groups	
		dTpa Group	Control Group
Boostrix *	dTpa	x	x
Placebo for dTpa vaccine	Placebo	x	x

**All eligible household contacts of the infants born to pregnant women enrolled in Spain will be eligible to receive a single dose of Boostrix as part of an assessment of cocooning.*

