- Control: placebo control
- Vaccination schedule:
 - All subjects will receive a single dose of *Boostrix* or placebo at 27-36 weeks (i.e. completed 27 weeks until 36 weeks) of gestation (Visit 1). Subjects who receive *Boostrix* at Visit 1 will receive a dose of placebo post-delivery (Visit 3) while those who receive placebo at Visit 1 will receive *Boostrix* post-delivery (Visit 3).
 - *All eligible household contacts of the infants born to pregnant women enrolled in Spain will be eligible to receive a single dose of Boostrix as part of an assessment of cocooning. Although the vaccine can be administered anytime during the study, it is recommended that the vaccine is administered preferably 2 weeks before birth of the infant.*
- Treatment allocation: randomised.
- Blinding: Observer-blind. Refer to Section 5.3 for details of the of blinding procedure.

The blinding of study epoch is presented in [Table 3](#).

Table 3 Blinding of study epoch

Study Epoch	Blinding
Epoch 001	observer-blind

- Sampling schedule: Blood samples will be collected at the following time-points:
 - Pre-Vacc (Visit 1): Before the booster vaccination, approximately 5 mL of blood sample will be collected from all subjects.
 - Post-Vacc (Visit 2): One month after the booster vaccination, approximately 5 mL of blood sample will be collected from all subjects.
 - Cord blood (Visit 3): approximately 2.5 mL of blood sample from the umbilical cord will be collected from all subjects.
- Type of study: self-contained
- Data collection: Electronic Case Report Form (eCRF).
- Safety monitoring: An independent data monitoring committee (IDMC) (including obstetrician, paediatrician, statistician and a neonatologist) will be put in place to oversee the safety aspects of *Boostrix* in the clinical study i.e. each SAE/congenital anomaly/foetal malformation case/incidence of grade 3 local and general solicited adverse events (AEs) will be reviewed by this committee (See Section 5.4.1 for details).

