#The procedures for household contacts can be performed anytime during the study, it is recommended that the vaccine is administered preferably 2 weeks before birth of the infant.

†The SAEs and pregnancies in household contacts should be reported from the date of vaccination till 30 days after vaccination.

The intervals between study visits are presented in [Table 6](#).

Table 6 Intervals between study visits (Amended: 15 July 2015)

Interval*	Optimal length of interval ¹	Allowed interval ²
Screening Visit → Visit 1	-14 to 0 days	-28 to 0 days
Visit 1 → Visit 2	30 days	21- 48 days
Visit 3 → Visit 4	60 days	45 - 75 days

¹. Whenever possible the investigator should arrange study visits within this interval.

². Subjects will not be eligible for inclusion in the ATP cohort for analysis of immunogenicity if they make the study visit outside this interval. In case a mother gives birth to an infant before 21 days post-vaccination, she will be excluded from the ATP cohort for analysis of immunogenicity.

*Household contacts can be vaccinated anytime during the study, it is recommended that the vaccine is administered preferably 2 weeks before birth of the infant.

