5.7.4. Biological samples evaluation

5.7.4.1. Immunological read-outs

The immunological read-outs are presented in [Table 9](#).

Table 9 Immunological read-outs

Blood sampling time-point		No. subjects	Component	Components priority rank
Type of contact and time-point	Sampling time-point			
Visit 1 (Day 0)	Pre-Vacc	All	PT, PRN and FHA	1
			D, T	2
Visit 2 (Day 30)	Post-Vacc	All	PT, PRN and FHA	1
			D, T	2
Visit 3 (At birth)	At birth	All*	PT, PRN and FHA	1

Pre-vacc: Blood sample to be collected before the dose of the booster vaccination in pregnant women (Visit 1).

Post-vacc: Blood sample to be collected one month after the booster vaccination in pregnant women (Visit 2).

* Cord blood collected from umbilical cord of subjects

In case of insufficient blood sample volume to perform assays for all antibodies, the samples will be analysed according to priority ranking provided in [Table 9](#).

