10.5. Derived and transformed data

- A seronegative subject is a subject whose antibody concentration is below the assay cut-off.

- A seropositive subject is a subject whose antibody concentration is greater than or equal to the assay cut-off defined (refer to [Table 8](#)). The following seropositivity thresholds are currently applicable:
 - Anti-PT, anti-FHA and anti-PRN antibody concentrations ≥ 5 EL.U/mL.
- A seroprotected subject is a subject whose antibody concentration is greater than or equal to the level defining clinical protection (refer to [Table 8](#)). The following seroprotection thresholds are applicable:
 - Anti-D antibody concentrations ≥ 0.1 IU/mL
 - Anti-T antibody concentrations ≥ 0.1 IU/mL.
- Other cut-offs to be considered:
 - Anti-D antibody concentrations ≥ 1.0 IU/mL.
 - Anti-T antibody concentrations ≥ 1.0 IU/mL.
- Vaccine response one month post vaccination in pregnant women (at Visit 3) to the diphtheria and tetanus antigens is defined as:
 - For initially seronegative subjects (pre-vaccination concentration below cut-off: < 0.1 IU/mL): antibody concentrations at least four times the assay cut-off (post-vaccination concentration ≥ 0.4 IU/mL).
 - For initially seropositive subjects (pre-vaccination concentration ≥ 0.1 IU/mL): an increase in antibody concentrations of at least four times the pre-vaccination concentration.
- Vaccine response one month post vaccination in pregnant women (at Visit 3) to the PT, FHA and PRN antigens, is defined as:
 - For initially seronegative subjects with pre-vaccination antibody concentration below cut-off, i.e. < 5 EL.U/mL: antibody concentrations at least four times the cut-off (post-vaccination concentration ≥ 20 EL.U/mL).
 - For initially seropositive subjects with pre-vaccination antibody concentration ≥ 5 EL.U/mL and < 20 EL.U/mL: an increase in antibody concentrations of at least four times the pre-booster antibody concentration, one month after vaccination.
 - For initially seropositive subjects with pre-vaccination antibody concentration ≥ 20 EL.U/mL: an increase in antibody concentrations of at least two times the pre-booster antibody concentration, one month after vaccination.
- The GMC calculations will be performed by taking the anti-log of the mean of the \log_{10} concentration transformations. Antibody concentrations below the cut-off of the assay will be given an arbitrary value of half the cut-off for the purpose of GMC calculation.

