**5.2.1.1. Elimination from ATP cohort for immunogenicity Excluded subjects**

A subject will be excluded from the ATP cohort for immunogenicity under the following conditions

Code	Condition under which the code is used
900	Questionable subject => Invalid informed consent or fraudulent data. In case informed consent is obtained retrospectively the subject is not eliminated.
1030	Study vaccine dose not administrated at all but subject number allocated => subjects enrolled but not vaccinated
1040	Administration of concomitant vaccine(s) forbidden in the protocol Previous vaccination containing diphtheria, tetanus or pertussis antigens or diphtheria and tetanus toxoids at any time during the current pregnancy.
1050	Randomisation failure (subject who received a vaccine not compatible with randomization)
1060	Randomisation code broken at the investigator site OR at GSK Safety department
1070	Site or route of study vaccine administration wrong or unknown.
1080	Vaccine has been administered (effective treatment number) despite a temperature deviation qualified by Status QA GMP NON Use.
1090	Vaccine has been administered (effective treatment number) out of the expiration date at the time of administration.
2010	Protocol violation linked to the inclusion/exclusion criteria including age and excluding codes mentioned below.
2040	Administration of any medication forbidden by the protocol
2050	Underlying medical condition forbidden by the protocol
2060	Concomitant infection related to the vaccine which may influence immune response
2070	Concomitant infection not related to the vaccine which may influence immune response
2090	Blood sample taken but non-compliance with blood sampling schedule for the cord blood sample (dates of BS not corresponding to adapted protocol intervals or unknown BS/vaccination dates) => Cord blood should be at least 21 days after vaccination
2100	Serological results not available for all antigens from the cord blood sample
2120	Obvious incoherence, abnormal serology evolution or error in data in cord blood sample (incoherence between CRF and results, wrong sample labelling.

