**6.3.2. Additional considerations**

Percentage of subjects with anti-D and anti-T antibody concentrations  $\geq 1.0$  IU/ml will be calculated along with its exact 95% CI by vaccine group at each visit.

For the distribution of antibody concentrations displayed using reverse cumulative distribution curves, the pre booster will also be included in the same graph as the one month after booster vaccination.

The distribution of antibody concentrations measured from the cord blood will also be generated in separated graphs.

The following descriptive analysis will be performed by sub-group of gestational age (27-32, 33-36 weeks of gestation of foetus at dose 1) and age of mother (18-24, 25-34, 35-45).

For each treatment group, before and one month after vaccination during pregnancy, cord blood sample and if blood sample result is available:

- Seroprotection rates and percentage of subjects with anti-D and anti-T antibody concentrations  $\geq 1.0$  IU/ml will be calculated along with and their exact 95% CIs for antibodies against diphtheria and tetanus.
- Seropositivity rates and their exact 95% CIs for antibodies against PT, FHA, PRN, will be tabulated.
- GMCs and their 95% CIs for antibodies against all vaccine antigens will be calculated.

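### A cord-blood result decides who enters the one-month maternal (Visit 2) ATP analyses, while no SAP elimination code checks the Visit 2 sample itself

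*SAP*

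**What the plan says.** **Sampling.** Protocol section 3 puts the one-month maternal sample at Visit 2: "Post-Vacc (Visit 2): One month after the booster vaccination, approximately 5 mL of blood sample will be collected from all subjects". SAP section 2 agrees. Visit 3 is birth, with the cord sample. Protocol Table 9 lists PT, PRN and FHA for cord blood, and lists D and T only for Visits 1 and 2.

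**Cohort.** SAP 5.1.3 and protocol 10.4.3 require results for "at least one study vaccine antigen component one month after vaccination i.e. Visit 3 in the cord blood sample", with cord blood collected at least 21 days after vaccination. SAP 5.2.1.1 applies this through code 2100, "Serological results not available for all antigens from the cord blood sample". Codes 2090 and 2120 also concern the cord sample. SAP 6.3.1 makes this cohort primary for immunogenicity, and Templates 10 and 12 name it for the one-month tables.

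**Visit 2 window.** Protocol Table 6 allows 21 to 48 days from Visit 1 to Visit 2, and its footnote says: "Subjects will not be eligible for inclusion in the ATP cohort for analysis of immunogenicity if they make the study visit outside this interval".

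**Vaccine response.** Protocol 10.5 states "Vaccine response one month post vaccination in pregnant women (at Visit 3) to the diphtheria and tetanus antigens is defined as" and uses the same visit for the pertussis antigens. SAP 11.2.4 restates both definitions without naming Visit 3.

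**Cord outputs.** SAP 6.3.1.1 limits them to PT, FHA and PRN. SAP 6.3.2 then introduces subgroup summaries with "For each treatment group, before and one month after vaccination during pregnancy, cord blood sample and if blood sample result is available". The list that follows includes D/T seroprotection, D/T percentages at 1.0 IU/ml or above, and GMCs for every vaccine antigen. Template 10 has cord rows for anti-D and anti-T.

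**The concern.** Immunogenicity one month after vaccination is a stated secondary objective with its own maternal sample. Admission to its primary analysis nevertheless turns on a different specimen, taken at a different time, that the estimates do not use. Valid paired maternal sera can be discarded because a cord sample was not obtained or gave no result.

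The sample that does matter is not screened by the codes. A Visit 2 draw outside its window triggers no elimination code, although the protocol says it should exclude the woman.

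Two smaller inconsistencies sit alongside. The protocol's vaccine-response visit contradicts its own sampling schedule. Some diphtheria and tetanus outputs are also requested from a specimen that is not assayed for them.

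**Working it through.** **1. The power statement, to see what is not affected.** Inputs from protocol 10.3 and Table 16: 272 evaluable women per group, one-sided alpha 0.025, null ratio 1.5, and for anti-PT an SD of 0.577 (log10) and a true ratio of 2.3.
- Difference: log10(2.3/1.5) = 0.1856.
- Standard error: 0.577 × √(2/272) = 0.0495.
- Power: Φ(0.1856/0.0495 − 1.960) = Φ(1.79) = 96.3%.
- FHA and PRN (SD 0.564, ratio 5) each exceed 99.9%, so 1 minus the sum of the three type II errors is 96.3%, which agrees with the stated figure of above 96%.
- 272/0.80 = 340 per group, as planned.

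This concerns the cord endpoint, for which a cord result is the right requirement. Nothing below changes it.

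**2. What the rules do to four kinds of woman** (delivery at day 21 or later, no other deviation):

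| Visit 2 sample | Cord result | By the SAP 5.2.1.1 codes | Used in one-month estimates? |
|---|---|---|---|
| Valid, day 21–48 | Yes | In ATP | Yes |
| Valid, day 21–48 | No | Out (code 2100) | No, though the data exist |
| Outside day 21–48 | Yes | In ATP (no code applies) | Yes, against protocol Table 6 |
| Missing | Yes | In ATP | No data to use |

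The second and third rows are the problem. The cord-result condition causes the exclusion, so relabelling the visit would not restore anyone.

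Code 2100 is also ambiguous. It can mean that no antigen has a result or that not every antigen has one, whereas SAP 5.1.3 asks for at least one. Read as requiring all five vaccine antigens it could not be met, because D and T are not assayed in cord blood.

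**3. Visits 2 and 3 are distinct in time.** Delivery at 280 days (protocol Appendix C) minus gestation at vaccination gives:
- 27 0/7 weeks: 280 − 189 = 91 days.
- 32 6/7 weeks: 280 − 230 = 50 days.
- 33 1/7 weeks: 280 − 232 = 48 days.
- 36 6/7 weeks: 280 − 258 = 22 days.

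With delivery at the due date, the whole 27–32 week stratum delivers after the 21–48 day window has closed.

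**4. Size.** The documents give no rate for a valid Visit 2 sample without a cord result, so a fraction f is assumed. Relative CI width is 1/√(1 − f), whatever the starting number. The last column is 10^(t × 0.577/√n), the multiplier and divisor for a one-group GMC. It borrows the anti-PT SD from Table 16 for illustration.

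| f | Lost of 340 per group | n | Relative width (log scale) | GMC CI factor |
|---|---|---|---|---|
| 0 | 0 | 340 | 1.000 | 1.152 |
| 5% | 17 | 323 | 1.026 | 1.157 |
| 15% | 51 | 289 | 1.085 | 1.166 |

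The base of 340 assumes that every randomised woman has a valid Visit 2 result, so the counts are upper values for each f.

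**5. The TVC trigger.** SAP 6.3.1 adds a TVC analysis when 5% or more of vaccinated subjects with serology are excluded in any group. If all 340 have serology and a missing cord result is the only reason for exclusion, 17/340 = 5.0% triggers it and 16/340 = 4.7% does not. Up to 16 women per group could then be left out with no supporting analysis.

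**The case against.** **The TVC analysis brings these women back.** Largely true. The TVC needs only one immunogenicity measure, and the whole assumed range of 5% to 15% meets the trigger. But it is a complement to the ATP analysis, does not run below 5%, and readmits women excluded for unrelated reasons. It is not a one-month ATP analysis.

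**The Visit 2 window is covered elsewhere.** SAP 5.1.3 does ask for compliance with protocol intervals, and mock Template 5 shows a 21-to-48-day column described as defining the ATP cohort. That supports the intention. The elimination codes still do not carry it out, and code 2090 is confined to the cord sample.

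**One cohort keyed to the primary endpoint is a legitimate choice.** It has the merit of drawing every table from the same women. That merit is partial, because the codes admit women without a Visit 2 result, so N can already vary by time point.

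**Early delivery costs nothing.** This stands. A woman known to deliver before day 21 has Visits 2 and 3 combined, outside the Visit 2 window, and Table 6 excludes her explicitly. The loss comes from absent cord results.

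**Stronger readings that a reader might infer.** One is that the protocol's Visit 3 label would leave D/T vaccine response missing for every woman and make the pertussis response a cord-to-maternal comparison. The documents do not support this:
- SAP 11.2.4 drops the label.
- SAP 6.3.1.1 places vaccine response with the before and one-month samples, and Template 12 counts women with both pre- and post-vaccination results.
- Where delivery precedes Visit 2, maternal blood is drawn at the combined visit before the cross-over dose (protocol 5.5 and 5.6.1.3.4).

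Another is that missed cord samples cluster in complicated deliveries and so bias the estimates. That is plausible, but neither document says so.

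**The D/T cord rows are harmless.** Mostly true. The templates are declared illustrative, and SAP 6.3.2 is conditional on a result being available. The likely outcome is empty cells.

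**Conclusion.** The point holds for the cohort definition. A woman with valid Visit 1 and Visit 2 sera but no cord result is excluded from the primary one-month maternal estimates for lack of a sample they do not use. The elimination codes leave the Visit 2 sample itself unchecked.

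The effect is mainly on who is analysed. At an assumed 5% to 15% loss, intervals widen by about 3% to 8%. These endpoints are descriptive under protocol 10.9 and SAP 7. It would be wrong to infer any threat to the primary objective.

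The Visit 3 label in protocol 10.5 is an error that SAP 11.2.4 has in effect corrected, but SAP section 9 does not record the change. The D/T cord outputs in SAP 6.3.2 and Template 10 are a minor mismatch with Table 9.

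This rests on the supplied protocol (Amendment 2). The SAP cites a later administrative change that was not available, but SAP section 9 mentions no added D/T assay on cord blood.

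**What to change.** Define ATP evaluability by time point:
- **Cord analyses:** a cord result at least 21 days after vaccination, as now.
- **One-month maternal analyses:** a Visit 2 result within 21 to 48 days for at least one antigen, plus a Visit 1 result for vaccine response, with no cord requirement.

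Apply codes 2090, 2100 and 2120 to each sample separately. State in code 2100 whether it means no antigen result or an incomplete set, consistent with the at-least-one rule. Give the Table 6 footnote the same time-point qualification. Show N per time point.

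In protocol 10.5, replace Visit 3 with Visit 2 in both vaccine-response definitions, and record the correction in SAP section 9. In protocol 10.4.3 and SAP 5.1.3, delete the words that equate the cord sample with one month after vaccination. Limit cord outputs in SAP 6.3.2 and Template 10 to PT, FHA and PRN.

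The cost is wording and some programming of flags by time point, with no new data. N will differ between the maternal and cord tables. If a common set of women is wanted, it can be shown as a supporting analysis.

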### 5.1.4. Total cohort for household contacts in Spain

Total cohort for household contacts will include all eligible household contacts of the infants born to pregnant women vaccinated in Spain. For the analysis of safety, all vaccinated household contacts will be considered.

## 5.2. Criteria for eliminating data from Analysis Sets

Elimination codes are used to identify subjects to be eliminated from analysis. Detail is provided below for each sets.

